This Project will try to elucidate the comprehensive impact that SHS and e-cigarettes emissions have on the European population and how health impacts vary according to socio-economic parameters with particular emphasis on specific vulnerable groups (patients suffering from pre-existing chronic lung diseases, heavy smokers, and other disadvantaged groups). Thus, we aim to develop and integrate implementation research on the determinants of SHS exposure, both assessed at the individual level and in the environment, the overall burden of disease caused (lung diseases and also cardiovascular diseases), including the specific respiratory health changes in patients and healthy people, the economic impact of both mortality and morbidity caused by these exposures, the methods to better characterize these exposures and novel interventions to reduce them. This will be achieved through a dedicated collaborative research effort involving expert, qualified scientists partnering a world class team to develop a comprehensive project to tackle secondhand tobacco smoke and e-cigarettes emissions.

GLOSSARY OF ABBREVIATIONS:

Abreviation	Term
TFRI	TobaccoFree Research Institute Ireland
DIT	Dublin Institute of Technology
FCTC	Framework Convention for Tobacco Control
ELF	European Lung Foundation
COPD	Chronic Obstructive Pulmonary disease
EU	European Union
SHS	Secondhand Smoke
CO Monitor	Carbon Monoxide Monitor
PEFR	Peak Expiratory Flow Rate
bpm	Beats per minute
RR	Respiratory Rate

Rationale & background information

Respiratory disease causes an important worldwide health burden. It is estimated that 235 million people suffer from asthma, more than 200 million people have chronic obstructive pulmonary disease (COPD), 65 million endure moderate-to-severe COPD, 1–6% of the adult population (more than 100 million people) experience sleep disordered breathing, 8.7 million people develop tuberculosis (TB) annually, millions live with pulmonary hypertension and more than 50 million people struggle with occupational lung diseases, accounting for more than 1 billion persons suffering from chronic respiratory conditions (GBD 2013 Mortality and Causes of Death Collaborators, 2014). In 2020, of 68 million deaths worldwide, 11.9 million will be caused by lung diseases, 4.7 by COPD, 2.5 by pneumonia, 2.4 by TB and 2.3 million by lung cancer.

Respiratory diseases burden the healthcare budgets within the European Union with direct costs of approximately €47.3 billion. Assuming a total EU expenditure on healthcare of approximately €800 billion (estimated from 9% of gross domestic product), the direct costs of treating respiratory diseases account for approximately 6% of the total EU healthcare budget. The four major respiratory diseases: COPD, asthma, pneumonia and TB have costs totaling €38.7, €17.7, €10.1 and €2.1 billion respectively (ERS, 2014).

Secondhand tobacco smoke (SHS) is a complex mixture of thousands of compounds including particulate matter emitted by the combustion of tobacco products and from smoke exhaled by smokers (IARC, 2004). It contains about 70 chemicals recognized as known and probable human carcinogens, other animal carcinogens, and many toxic and irritant agents (US Department of Health and Human Services, 2006). Over the past two decades, scientific evidence has accumulated linking SHS exposure to adverse health outcomes, including respiratory outcomes in children and adults, acute cardiovascular effects, and lung cancer (IARC, 2004; Ott et al., 2006; US Department of Health and Human Services, 2006). Most of this evidence is based on long-term SHS exposure research (IARC, 2004). Some recent studies have also reported evidence of effects following short-term exposure to tobacco smoke, such as eye irritation and respiratory irritation among non-smokers (Junker et al., 2001). Even brief and short-term exposures to SHS may generate significant adverse effects on the human

respiratory system (Flouris and Koutedakis, 2011). Finally, the effects of acute exposure to tobacco smoke on cardiac autonomic function may contribute to pathophysiological mechanisms linking exposure to SHS to increased risk of cardiovascular mortality (Pope, III et al., 2001).

Smoke-free policies have been expanding worldwide since the World Health Organization (WHO) encouraged countries to follow Article 8 of the Framework Convention on Tobacco Control (FCTC) (WHO 2003) to protect people from SHS (Globalsmokefree Partnership, 2009). Legislation has been widely implemented in indoor public places, workplaces, and public transportation (WHO, 2009). Since the implementation of indoor smoke-free environments, several studies have demonstrated important reductions of SHS exposure, including an 80–90% decrease in previously high-exposure settings, such as workplaces and hospitality venues like bars and restaurants (IARC 2008). However, indoor smoking restrictions may increase the likelihood that smokers will gather at convenient outdoor locations such as public areas near building entrances (Kaufman et al. 2010a). In 2007, a revision of the FCTC Article 8 guidelines further recommended that quasi-outdoor and outdoor public places should be smoke-free under some circumstances, and called upon countries to “adopt the most effective protection against exposure wherever the evidence shows that hazard exists” (WHO 2009). Recently, some countries have extended smoking bans to some outdoor locations (Globalsmokefree Partnership 2009; Repace 2008), particularly health care centers and settings where children are present (Globalsmokefree Partnership 2009). However, there remain some outdoor locations close to smoke-free areas where people may be exposed to SHS, such as terraces and patios in hospitality venues and near entrances to smoke-free buildings (Globalsmokefree Partnership 2009).

Some controversy exists regarding whether smoking should be prohibited in outdoor settings (Chapman, 2008; Thompson et al., 2008). Health concerns about SHS exposure, nuisance from SHS, litter, fire hazards, concern about establishing positive smoke-free models for youth, and reducing youth opportunities to smoke (Bloch and Shopland, 2000; Brennan et al., 2010; Cameron et al. 2010; Chapman, 2008; Repace, 2008; Thompson et al., 2008; Thomson et al. 2009) exemplify the reasons why smoking should be banned in selected outdoors locations. Outdoor smoking bans might also support smokers who are trying to quit by limiting their

overall cigarette consumption (Williams et al., 2009). Selected outdoor smoking bans should also help to denormalise smoking in outdoor areas (Thompson et al., 2008). In a number of jurisdictions, the majority of the public supports restricting smoking in various outdoors settings, and this support appears to be increasing over time (Thomson et al., 2009). However, those who oppose outdoor smoking bans argue that it is ethically unsustainable because it does not respect the principle of freedom and autonomy of individuals, and that there is insufficient evidence that SHS in these environments has an impact on health (Chapman, 2000; Chapman, 2008). Outdoor SHS has been scarcely evaluated. It has been hypothesized that the introduction of indoor smoking bans has led to a relocation of smokers to outdoor areas, with a subsequent increase of tobacco smoke levels in outdoor places (Sureda et al., 2011).

SHS exposure has been commonly studied in different indoor locations, especially in workplaces such as hospitality venues or health care centers (IARC, 2009); mainly before launching smoke-free legislation or, in a few countries, for the evaluation of smoke-free laws. In the US, it is estimated that SHS exposure causes more than 41,000 deaths among nonsmoking adults and 400 deaths in infants each year, and approximately \$5.6 billion annually in lost productivity. Although population exposure to SHS has declined over the past two decades (Homa et al., 2015), many non-smokers remain exposed to SHS in workplaces, public places, homes, and vehicles (Max et al., 2012). The Eurobarometer survey has incorporated a few questions on exposure to secondhand smoke in recent editions, and previous work from some of the TackSHS partners have studied the exposure to secondhand smoke in some European countries to be between 20 and 60% of the non-smoker population, both using a population- based approach and cross-sectional surveys [Lukshenkova et al., 2008; Martínez-Sánchez et al., 2009; Sureda et al., 2014 (TackSHS Spanish partner) in Spain, Gorini et al., 2008; Martínez-Sánchez et al., 2012; (TackSHS Italian partners) in Italy, Wallner et al., 2010 in Austria, Vardavas et al., 2012 (TackSHS Greek partner) in Greece, Goodman et al., 2007 (TackSHS Irish partner) in Ireland], or performing environmental measures of particulate matter or airborne nicotine as SHS markers [Semple et al. 2007 (TackSHS UK partner) in Scotland, Schneider et al., 2008 et al. in Germany, Vardavas et al., 2014 (TackSHS Greek partner) in Greece, and Nebot et., 2005 and Lopez et al., 2008 in 8 countries in previous SANCO and FP7 projects.

An inclusive understanding of the exposure to SHS in European populations and its societal mortality, morbidity and economic burden is however lacking. *A comprehensive survey using validated questions across countries will provide an actual picture of the exposure to this hazard, with the possibility to compare countries with different income and vulnerable groups, such as people with chronic diseases, and specifically chronic pulmonary diseases.* Moreover, we will be able to gain information about the attitudes of the population towards SHS, and the degree of agreement with smoke-free legislation. In addition to the survey, we aim at objectively measuring markers of secondhand smoke in non-regulated settings such as private places and outdoor public places. In a recent review of 18 studies that assessed secondhand smoke levels (Sureda et al. 2013), we found that SHS levels in outdoor smoking areas were not negligible, especially in areas that are semi-enclosed. This review clearly indicated the potential for high SHS exposures at some outdoor settings and indoor locations adjacent to outdoor smoking areas. We showed, moreover, that high smoker density, highly enclosed outdoor areas, low wind conditions, and close proximity to smokers generate higher outdoor SHS concentrations. *Thus, our aim in the TackSHS project is to perform new measurements in the same countries where we will be conducting the survey –hence with the possibility to compare individual perceptions and assess concentrations of SHS markers-- and to take into account those factors that modify the exposure.* Moreover, the project will quantify the proportion of Europeans exposed to secondhand tobacco smoke, thus enabling the estimation of the morbidity and mortality attributable to this hazard, and to estimate its economic burden by means of “Social Return on Investment” models.

Since 2007, the popularity of **electronic cigarettes (e-cigarettes)** has grown rapidly around the world. Among the general population of the United States (US) (King et al., 2013) the prevalence of ever-use, according to a web-based survey, showed a twofold increase between 2010 and 2011 (from 3.3% to 6.2%). Double similar scale of increase was also observed in US adolescents (Dutra and Glantz, 2014) and in middle and high school students (MMWR, 2013) between 2011 and 2012. In Europe, there is certain variability in the prevalence of use among studies, depending on the population and the questions used in the surveys (Dockrell et al., 2013; Goniewicz et al., 2012; Doupcheca et al., 2013; Mar-tínez-Sánchez et al., 2014). Using data from the 2012 Eurobarometer, Vardavas et al. 2014 (TackSHS Greek partner) showed that 7% of the European citizens have tried the e-cigarettes with experimentation significantly

higher among current smokers. In Italy, a survey conducted by Gallus et al. 2014 (TackSHS Italian partner) showed that awareness of e-cigarettes was 91.1%, lowest among some vulnerable populations such as women, the elderly, and less educated subjects. In Italy, ever e-cigarette use was 6.8% overall and was inversely related to age, whereas no difference was observed according to sex. In Spain, studies from the TackSHS coordinators found an awareness of e-cigarettes lower than in Italy (82.3%) but a similar prevalence of ever e-cigarette use of 6.5% (1.6% current use, 2.2% past use and 2.7% only e-cigarette experimentation) and the predominant ever and current e-cigarette use was among current smokers (75% of ever e-cigarette users were current smokers) (Martínez-Sánchez et al. 2014a and 2014b)

Finally, reducing population exposure to secondhand tobacco smoke is a significant health priority. While evidence suggests that there has been an increase in the percentage of smokefree homes from 16% in 1998 to almost 50% in 2008 in England and Wales (Jarvis et al., 2012), and data from Scotland indicate that about 12% of children are regularly exposed to second-hand smoke within their own home (Akhtar et al., 2007). This is particularly the case for children living in socioeconomically disadvantaged communities (Akhtar et al., 2009). Even though families across all levels of deprivation have shown increased restrictions towards reducing SHS exposure in their homes, homes with greater disadvantage tend to have fewer restrictions (Phillips et al., 2007). The Scottish Government is the first country in the EU to introduce a national target with the aim of reducing the proportion of children exposed to second-hand smoke by one-half by 2020. There is a clear and significant challenge to the public health community on how to deliver reductions in both frequency and intensity of children's exposure to SHS, particularly within socio-economically deprived communities. One known effective motivational tool in aiding change in smoking behaviour is the use of instruments to measure levels of PM2.5 as a marker of SHS, with some recent qualitative work suggesting that personalized biofeedback of exposure to SHS may be a key motivator to household smoking behaviour change (Jones et al., 2011). Additionally, there is evidence from the occupational health literature that suggests that measurement and feedback of information on personal exposure to hazards can help change behavior (Rosen et al., 2005). Thus, feedback on air quality within the home setting could work as a powerful tool to change the perceptions and behaviours of smokers. The Scottish partner of TackSHS used personalised feedback of PM2.5

values in addition to other methods aimed at reducing children's SHS exposure (the REFRESH intervention) (Wilson et al., 2013). This feasibility study of an air quality feedback behavioural intervention was based on the evidence that people can make changes in response to receiving personalised health-based data along with evidence suggesting some effectiveness in reducing SHS exposure through counseling.

Study goals and objectives

The project objectives are:

- To Measure Respiratory Health effects when exposed to SHS in
 - Patients with Asthma
 - Patients with COPD
- Exposure levels to Second Hand Smoke (SHS) in smoking areas provided by Bars Casinos and Bingo halls etc.

Study Design

Population:

The study population will consist of 30 Asthmatic and 30 Chronic Obstructive Pulmonary Disease (COPD) subjects to be recruited through the European Lung Foundation (ELF) in Hungary Spain and Ireland. (20 subjects in each country)

Inclusion criteria for each patient group:

Confirmed [name] COPD patients

- Current or ex-smokers.
- Fully ambulatory.
- Frequent smoking areas*
- Between 50yrs and 70yrs

Confirmed [name] patients

- Fully ambulatory
- Frequent smoking areas
- Over 18yrs

*Irish law has defined an outdoor smoking area as: A place or premises, or part of a place or premises that, is wholly uncovered by any roof, fixed or mobile. An out door place or premises that is covered by a roof, so long as not more than 50% of the perimeter (outside) is covered by a wall, windows, gate or similar.

Exclusion criteria:

- Under 18yrs
- On Oxygen therapy
- Never smokers in COPD patient group
- Undergoing treatment for acute exacerbations.
- Pregnant women

Primary Endpoints:

- To monitor personal exposure to SHS in areas exempted from legislation in pubs, bars and casinos etc. using novel monitoring technologies.
- To simultaneously monitor the respiratory effects as indicated by changes in respiratory rate and flow and activity levels.

Secondary Endpoints

- Any increase in medication usage
- Unscheduled Primary Care /Hospital visits
- Breath Carbon Monoxide (CO) monitoring pre and post study
- Spirometry pre and post exposure

Ethics:

Ethical approval will be sought from DIT Ethics Committee prior to beginning of the project. All documentation relating to the project will be provided for ethical review. There are no perceived Ethical issues as patients will be fully informed and there will be no intervention other than monitoring. It was considered that requesting subjects to go into outside smoking areas might be a problem so only subjects who already frequent such areas will be recruited.

All participants will be provided with a patient information leaflet and asked to sign an informed consent form. (Appendix 1)

Methodology:

Recruitment

Relevant patient organisations will be identified in each country through European Lung Foundation (ELF) ([name]) and project partners.

Patients will be contacted through ELF national organisation with input from national/project partners. Inclusion and exclusion criteria, Information sheet and a short recruitment questionnaire (Appendix 1 and 2) will be distributed to possible patient volunteers.

Consent:

Once eligibility has been determined patients will be given an appointment (in a research room either Clinic/Hospital or University based, venue to be confirmed) where they will receive an information leaflet. Once this has been read and any concerns of the participant addressed and explained, they will then be asked to provide written consent prior to their study enrolment. Consent will be obtained from all participants. Consent is on-going and participants can revoke consent at any stage of the project. (Appendix 1)

Technicians and researchers will be trained in the use of monitoring devices by TFRI staff. The 60 patients will be fitted with equipment which will measure their exposure to pollutants including Secondhand smoke as well as measuring the effects on their breathing rate.

Devices used to gather data:

Carefusion CO Monitor

The CO Monitor features single-button operation and coloured light indicators to simplify patient understanding of the process: (Appendix 3)

- Green: 0 to 6ppm
- Amber: 7 to 10ppm
- Red: 11 to 20ppm
- Flashing red and alarm: >20ppm

Spirometer:

Spirometry measures the volume of air that the patient is able to expel from the lungs after maximal inspiration.

Spirometry is invaluable as a screening test of general respiratory health, similar to BP measurement in cardiovascular disease. It is a reliable method of diagnosing and differentiating between obstructive airways disorders (e.g. COPD, asthma) and restrictive diseases (where the size of the lung is reduced, e.g. fibrotic lung disease).

Spirometry can also be used to determine the severity of asthma and COPD. This is important because the severity of these diseases cannot be predicted simply from the clinical signs and symptoms. The FEV₁ is the maximal volume of air exhaled in the first second of a forced expiration from a position of full inspiration (expressed in litres at BTPS). The forced vital capacity (FVC) is the maximal volume of air exhaled with maximally forced effort from a maximal inspiration (expressed in litres at body temperature and ambient pressure saturated with water vapour – BTPS).

RESpeck:

RESpeck is a monitoring device, which collects data via low power wireless link for processing at base-station in patient's home. RESpeck had been verified to be a reliable measure of RR when compared with RR derived from a nasal cannula in anaesthetised post-operative patients; instantaneous RESpeck RR matched the routine clinical measurement of RR within two breaths per minute (bpm) an acceptable limit of accuracy employed previously—on 86 % of occasions, with a mean absolute difference of 0.6 bpm. (15. Drummond GB, Bates A, Mann J, Arvind DK. Validation of a new non-invasive automatic monitor of respiratory rate for post-operative subjects (Br J Anaesth. 2011;107:462–469. doi: 10.1093/bja/aer153). It will be transmitted to a server at the Centre for Speckled Computing via broadband internet where the data will be analysed. RESpeck files will be downloaded from the iPod or Android tablet and the gross activity and breathing signals will be plotted. The raw data files will then be processed post hoc using proprietary software (University of Edinburgh), which produces a separate file containing time and validated RR data. The software will actively exclude any data captured in excess of a pre-defined movement threshold. This means that only the fine movements associated with breathing will be analysed, and that larger movements not associated with breathing will be omitted. The number of validated breaths captured before, during and after exposure to SHS will be noted. The maximum, minimum and mean number of validated breaths captured before and after SHS exposure per minute will also be calculated; zero data (i.e. where no validated breaths are produced per minute) will be included in the mean data. Finally, maximum, minimum, and the mean (± 1 SD) RR will be recorded. (Appendix 4),

AIRSpeck:

AIRSpeck Personal/mobile monitor will be used for exposure measurements (Appendix 5)

- Includes humidity sensor and improved WiFi range
- Detect indoor fine particulate matter (dust, smoke, exhaust, etc.)
- Plot trends over time with our free visualization tools
- Access your home's data from your smart phone or computer anywhere, anytime
- Compare indoor and outdoor* air quality readings on screen

Patient Schedule:

Each patient will visit the centre on 2 occasions the first at enrolment and training in use of equipment, this should be at least 2 to 4 hours prior to exposure. The second will be at least 24hrs post exposure to secondhand smoke at, at least one outing to an outdoor smoking area. The duration of time to be spent in the outdoor smoking area is to be a minimum of 15 mins with a preferable time of 30-60 mins.

Spirometry and Breath Co are to be done for at least 2 to 4 hours prior to exposure and 24 hrs post exposure, at the second visit to the research centre.. At the follow up visit all data will be downloaded and checked and any anomalies will be addressed and clarified with the patient.

National Partners will be trained in the use of devices measuring exposure using AirSpeck and respiratory rate using RESpeck. Data will be transmitted to server at the Centre for Speckled Computing via Internet or mobile phone technology where the data will be analysed.

Subsequently patients in each of 3 countries will be shown how to wear and carry the personal monitor devices , ensuring data is recorded.

Data collection, analysis and report writing: This will be carried out by TFRI in collaboration with Project Partners and in consultation with [name].

Table of tasks

	Baseline visit Minimum of 2 to 4 hrs pre exposure	Post exposure visit Minimum 24hrs post exposure
Consent and information sheet	✓	
Recruitment Questionnaire	✓	
CAT/ACT form	✓	
CO Reading	✓	✓
Spirometry	✓	✓
Training of fitting and use of Respiratory device	✓	
Training and fitting of Particle monitor	✓	
Retrieve equipment and check data recorded		✓
Check patient entries and resolve any data queries		✓
Download data and send to TFRI		✓
Check devices working correctly for next subject		✓

Other support for the Project:

[name]

ELF

Asthma society Ireland

Advisory Panel: Tack Project Partners:

[name]

[name]

[name]

[name] [name]

[name] [name]

[name]

Safety Considerations

The safety of all research participants will be considered at all times, they will be seen in an insured medical practice. All personnel dealing with patients will be fully trained and insured.

The Project will be registered at www.clinicaltrials.com

Data Management and Statistical Analysis:

All data will be stored on a secure server and will be de-identified. Data will be entered giving each participant a unique identifier code; neither their name, address nor date of birth will be recorded in order to protect the confidentiality of the participant. Analysis will be carried out on a blinded dataset using SPSS. Data will be presented as mean and standard deviation (\pm SD) for continuous variables, or percentage for qualitative variables, as appropriate, or their 95% confidence interval. Differences within groups will be compared with Chi² tests for categorical

variables and Student t test for continuous variables. A p value lower than 0.05 will be considered statistically significant.

Quality Assurance:

Baseline and post exposure data re CO readings, Peak flows any change in medication usage or unscheduled hospital or Dr visits will be entered at source and will be verified by the clinical nurse specialist. Patients will be asked to keep a record of any increase medication usage as well as document any Doctor or Hospital visits as well as description of outdoor smoking area visited. (Appendix 6)

All digitally recorded data will be downloaded from the device to a secure server. A Post Doc and or a Research assistant working with TFRI with advice from partners will further examine study data. Any anomalies found will be addressed and resolved from source data.

Expected Outcomes of the Study

- Exposure levels in the home
- Exposure levels in Smoking areas
- Respiratory symptoms pre and post exposure

Dissemination of Results and Publication Policy:

It is intended that research findings will be published in the form of peer reviewed research articles in first-line high impact or open access journals, and also the presentation of the main results in international tobacco control conferences, such as the European Tobacco or Health Conference, or the Annual or the European Meetings of the Society for Research in Nicotine and Tobacco. There will be a final TackSHS conference in which the main findings will be presented to patients, stakeholders, and policy makers. Together with this, dissemination materials (i.e., factsheets, press releases) will be produced and published in

the TackSHS website as well as disseminated through the websites of the collaborating partners and stakeholders. The results will also be EU deliverables for TackSHS project.

Problems Anticipated:

Recruitment

Co-operation of partners in Spain and Hungary at the appropriate time.

Lag time of symptoms post exposure.

Proof of smoking on site, photograph of venue will be needed to verify this

Translation and local adaption of documents

Project Management

[name] is WorkPackage 5 Leader.

[name] will be responsible for the management of the project, obtaining consent of all participants in the project, project equipment and gathering and safety of all data. A Post Doc and research assistant working with TFRI will aid in verifying validity of data and the statistical analysis.

Duration of the Project:

The project is to run for a 4-year period starting November 2015 and completion is expected by October 2019.

Gantt chart

Due Month Number	12	13	14	15 to 30	48
Protocol					
Local Ethical approval					
Study registration number					
Ethical approval of Spain and Hungary					
National Level Training in use of sensors					
Recruitment and data collection					
Report of Results					

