The second monitor was the RESpeck RR sensor (University of Edinburgh Department of Speckled Computing, School of Informatics, Scotland), which was an encapsulated tri-axial accelerometer positioned on the left side of the abdomen just under the costal margin. RESpeck recorded changes in abdominal position in three orthogonal axes, relative to gravity. These data were automatically integrated and differentiated into a derived ‘activity’ signal, and a RR signal with a shape similar to inspiratory and expiratory flow. RESpeck had been verified to be a reliable measure of RR when compared with RR derived from a nasal cannula in anaesthetised post-operative patients; instantaneous RESpeck RR matched the routine clinical measurement of RR within two breaths per minute (bpm)—an acceptable limit of accuracy employed previously—on 86 % of occasions, with a mean absolute difference of 0.6 bpm [15]. However, our study was the first time that RESpeck had been implemented in the pre-hospital environment. RESpeck was entirely wireless and all data were transmitted using a Bluetooth 4.0 Low-Energy protocol to an iPod (Apple, Cupertino, CA, USA) on which the data were displayed and recorded. Accelerometer data were recorded at a rate of 12.5 Hz. Figure 2 displays both

medical sensors and their method of attachment to the body.

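### Primary endpoint 2 reads outing-related changes in activity and respiratory rate as smoke effects, with no smoke-free comparison or activity adjustment, and defines no flow summary

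*Combined protocol and SAP*

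**What the plan says.** Under Primary Endpoints, the protocol sets out "To simultaneously monitor the respiratory effects as indicated by changes in respiratory rate and flow and activity levels". The three markers are RR, flow and activity, all to be followed during exposure.

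The RESpeck section under Devices used to gather data says that activity and breathing signals will be plotted. The raw files then go through software "which produces a separate file containing time and validated RR data". On movement it states: "The software will actively exclude any data captured in excess of a pre-defined movement threshold". Validated breaths are counted before, during and after exposure. Per-minute counts are summarised before and after, with minutes that yield no validated breath counted as zero. Maximum, minimum and mean RR are also recorded.

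On flow, the device slides in Appendix 4 list a combined effort/flow output. Section 2.5 of the ambulance study reproduced there describes "a RR signal with a shape similar to inspiratory and expiratory flow". Spirometry is a secondary endpoint, "Spirometry pre and post exposure", and Patient Schedule confines it to the two visits: "Spirometry and Breath Co are to be done for at least 2 to 4 hours prior to exposure and 24 hrs post exposure". Quality Assurance also mentions "Baseline and post exposure data re CO readings, Peak flows", again at baseline and after exposure.

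Patient Schedule asks for at least one outing to a smoking area, of at least 15 minutes and preferably 30 to 60. It describes no smoke-free outing. Data Management and Statistical Analysis gives a within-group Student t test at 0.05, without covariates.

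**The concern.** A before/during/after contrast within one outing estimates the effect of everything that differs between the periods. A patient travels, walks in, sits or stands and talks, then leaves. Activity changes at each step whether or not anyone is smoking, and exertion can carry over into RR. The endpoint wording assigns all of this to smoke.

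At stake is the interpretation of one of two primary endpoints. Lower activity on sitting down could be reported as harm. Recovery from walking could mimic or hide a change in RR. A change in validated-breath counts could be read as a change in breathing when it reflects how much the patient moved. Flow could not be reported as planned, because nothing says what number represents it.

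**Working it through.** The plan gives no power or effect-size figure to reproduce, so the check is mainly a comparison of sections. The arithmetic only shows orders of magnitude.

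**1. Activity.** It is recorded and plotted. No summary, smoke-free comparison or adjustment is given. Outing and smoke coincide, so their effects on activity cannot be separated.

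**2. RR.** The endpoint implies a contrast of RR between periods, analysed by an unadjusted t test. The filter drops data above a threshold whose value is not given. It acts on movement at the time, so a patient who has just walked in and sat down passes it while RR may still be raised. Appendix 6 logs exposure times, walls, smoker counts and unusual events, but has no field for posture or activity.

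**3. Validated-breath counts.** Section 3.4 of the ambulance study reports 60% of data excluded on average, with a range of 27.4% to 86.5% across patients. It reports 29 validated breaths in transit (from 3 of 11 patients) against 765 at nominal rest (from 14). Time in each state is not given with these counts, so they are not rates.

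- If counts are roughly proportional to the retained share (an assumption), two recordings at the same true RR but at the two ends of that range differ by (1 − 0.274)/(1 − 0.865) = 0.726/0.135 = 5.4 times.
- Retained minutes = stay × (1 − share excluded), assuming the ambulance shares carry over:

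| Stay | 27.4% excluded | 60% | 86.5% |
|---|---|---|---|
| 15 min | 10.9 | 6.0 | 2.0 |
| 30 min | 21.8 | 12.0 | 4.1 |
| 60 min | 43.6 | 24.0 | 8.1 |

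**4. Flow.** The waveform is recorded during the outing, but the processed file holds time and RR. Every listed summary is a breath count or an RR statistic. Spirometry falls outside the exposure window and belongs to another endpoint.

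**5. Illustration of the RR consequence.** Assumptions: true smoke effect zero; paired two-sided t test at 0.05 (the plan states neither pairing nor sidedness); activity-driven shift b in mean RR; SD of paired change s of 2 to 4 bpm. The documents supply neither b nor s. Noncentrality = b√n/s with n − 1 degrees of freedom. For b = 1, s = 2, n = 30 it is √30/2 = 2.74, giving probability 0.75. Chance of p < 0.05:

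| b (bpm) | n = 30, s = 2 / 3 / 4 | n = 60, s = 2 / 3 / 4 |
|---|---|---|
| 0 | 5% / 5% / 5% | 5% / 5% / 5% |
| 0.5 | 26% / 14% / 10% | 48% / 25% / 16% |
| 1 | 75% / 42% / 26% | 97% / 72% / 48% |
| 2 | >99% / 94% / 75% | >99% / >99% / 97% |

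A shift in this range would arise, for example, if 25% to 50% of retained 'before' time were recovery time with RR 3 bpm above seated RR: 0.25 × 3 = 0.75 and 0.50 × 3 = 1.5 bpm. These inputs are also assumed.

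**The case against.** The strongest reply concerns flow. RESpeck is worn through the outing, and Appendix 4 names rate, effort/flow and activity among its outputs, which match the endpoint's three markers. The endpoint asks for changes, so an uncalibrated relative signal could serve. This stands. A reader might infer that no patient will have any flow measurement during exposure, but the documents do not support that. What is missing is a defined summary of a signal that is recorded. The mention of peak flows is a minor labelling matter about clinic data.

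Second, the filter may be strict. The ambulance study's discussion says that clinicians stepping in and out of the vehicle was enough to stop validated output. This also stands: concurrent gross movement is largely dealt with. Because the threshold is not given, one cannot claim that light movement stays in the RR data. Recovery after walking is not addressed, and a strict filter makes breath counts more dependent on movement.

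Third, walking on both sides of the exposure could partly cancel in a before-versus-after contrast. That is possible, but nothing in the plan arranges it, and it does not help a comparison with the exposure period itself.

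Fourth, equipment is retrieved at least 24 hours after exposure, so later activity may also be recorded and could respond to smoke. It is therefore too strong to say that activity could never show an effect. Attribution still fails, because no comparison period is specified.

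Finally, the ambulance figures include vehicle transit and describe data excluded, not biased data retained. They show that the sensor's yield depends on movement and cannot predict this study's yield.

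**Conclusion.** The point holds as one of attribution and specification. Under the plan, a change in activity cannot be credited to SHS. RR is open to bias from activity, reduced but not removed by the filter. Validated-breath counts should not be read as a respiratory effect. Flow during exposure has a recorded waveform but no defined summary.

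Two stronger readings should be resisted. One is that two of the three markers are empty or cannot show any effect: both are recorded, and the gap lies in the definition and the comparison. The other is that RR will be wrong by a stated number of bpm. The shifts and SDs above are assumed, and the documents quantify neither. The 0.6 bpm device agreement quoted in the RESpeck section comes from anaesthetised post-operative patients and is no yardstick for bias in a group mean.

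The conclusion rests on the structure of the plan and on the inference that going out, walking and sitting alter activity, and through it RR. It does not depend on the illustrative figures. This is a worthwhile, inexpensive improvement to a primary endpoint.

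**What to change.** - Make change in RESpeck RR the primary respiratory measure.
- Use the recorded activity signal to match or adjust the RR minutes that are compared. Report activity descriptively, not as an SHS effect.
- Report validated-breath counts as data yield only.
- Log about 5 minutes of quiet sitting at three times on Appendix 6: before exposure, in a smoke-free place and after a rest long enough to recover from walking; in the smoking area; and after leaving it, again after a rest. Compare RR across these periods. The initial rest matters, because a baseline taken on arrival would capture the recovery it is meant to avoid.
- For flow, either pre-define a relative RESpeck effort/flow metric or leave flow to the existing spirometry secondary endpoint.

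Cost: endpoint and analysis wording, one patient instruction and three time boxes on Appendix 6. Devices and visits stay the same, and 5 minutes fits within the 15-minute minimum stay. Behaviour is slightly less natural for a few minutes. Order and time effects remain, because this adds no smoke-free outing.
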